- (1) To determine if a relatively brief, focused intervention in reappraisal-by-distancing in bereaved spouses engages the targeted mechanisms. Hypotheses: Distancing training is expected to result in longitudinal reductions in self-reported negative affect, increases in RSA, and changes in neural activity in a priori ROI's above (i.e., reductions in amygdala activity, increases in DLPFC activity) that are greater than those for reinterpretation training.
- (2) To examine the impact of changes in the targeted mechanisms in changing health-relevant behavior. Hypotheses: Across time and participants, reductions in self-reported negative affect, increases in RSA, and changes in neural activity are expected to lead to reductions in depressive symptoms and grief rumination.
- (3) As an exploratory aim, to mechanistically relate intervention effects to behavior change as a function of changes in the targeted processes. Crucially, this aim will also include assessment of interactions with age and gender of the bereaved spouse and initial depression and grief severity.

Hypotheses: Distancing training will lead to reductions in grief rumination and depression that are mediated by changes in the targeted neurobiological and behavioral mechanisms.

Sample Size::

84 bereaved participants will be recruited (i.e., N=42 per each intervention cell) and randomly assigned to receive either Distancing Training or Reinterpretation Training.

Power Analyses:

Outcome: Self-reported negative affect

Sufficient power to assess self-reported negative affect outcomes will be achieved by recruiting 42 participants per training cell. This sample size estimate is based upon a power analysis using an approximate effect size ($d=.70$) previously reported for within and between-subjects behavioral analyses of longitudinal reappraisal training data¹. Power analyses using this approximate effect size indicate over 95% power ($\alpha=.05$) to detect within-group effects and 90% power ($\alpha=.05$) to detect between-group effects should be achieved with 36 participants per cell. Assuming all-cause attrition of 15% (which reflects a liberal upper bound given past participant attrition rates of approximately 10%), the proposed sample size should provide sufficient power to assess this outcome. Post-attrition, we expect to have analyzable complete data for approximately 36 participants per cell.

Outcome: Respiratory sinus arrhythmia (RSA)

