Sufficient power to assess respiratory sinus arrhythmia outcomes will be achieved by recruiting 42 participants per training cell. This sample size estimate is based upon a power analysis using an approximate effect size ($d=.70$) previously obtained for within and between-subjects analyses of RSA data². Power analyses using this approximate effect size indicate over 95% power ($\alpha=.05$) to detect within-group effects and 90% power ($\alpha=.05$) to detect between-group effects should be achieved with 36 participants per cell. Assuming all-cause attrition of 15% (which reflects a liberal upper bound given past participation attrition rates of approximately 10%), the proposed sample size should provide sufficient power to assess this outcome. Post- attrition, we expect to have analyzable complete data for approximately 36 participants per cell.

Outcome: Neural activity (fMRI)

Sufficient power to assess neural activity outcomes will be achieved by recruiting 42 participants per training cell. This sample size estimate is based upon a power analysis using a within-subject fMRI effect size estimate for right amygdala affective reactivity from a recent large-scale meta-analysis of fMRI effect sizes using Human Connectome Project data³ of approximately $d=.70$. This effect size estimate is also appropriate for between-subjects neural effects⁴. Power analyses using this approximate effect size indicate over 95% power ($\alpha=.05$) to detect within-group

effects and 90% power ($\alpha=0.05$) to detect between-group effects should be achieved with 36 participants per cell. Assuming all-cause attrition of 15% (which reflects a liberal upper bound given past participation attrition rates of approximately 10%), the proposed sample size should provide sufficient power to assess this outcome. Importantly, this sample size will also account for any participant data loss due to excessive scanner motion (despite mitigation efforts to avoid this), task non-response in the scanner, and poor signal-to-noise in MR signal, in addition to participants dropping out of the study. Each of these classes of participant attrition is expected to be rare. Thus, post-attrition from all causes, we expect to have analyzable complete data for approximately 36 participants per cell.

Outcome: Depressive symptoms, grief rumination, perceived stress, and reappraisal usage frequency.

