Sufficient power to assess questionnaire outcomes (i.e., depressive symptoms, grief rumination, perceived stress, and reappraisal usage frequency) will be achieved by recruiting 42 participants per training cell. This sample size estimate is based upon a power analysis using an approximate effect size ($d=.70$) previously reported for within and between-subjects analyses of questionnaire reports measuring these variables (e.g., depressive symptoms²; perceived stress¹). Power analyses using this approximate effect size indicate over 95% power ($\alpha=.05$) to detect within-group effects and 90% power ($\alpha=0.05$) to detect between-group effects should be achieved with 36 participants per cell. Assuming all-cause attrition of 15% (which reflects a liberal upper bound given past participant attrition rates of approximately 10%), the proposed sample size should provide sufficient power to assess this outcome. Post-attrition, we expect to have analyzable complete data for approximately 36 participants per cell.

Definitions of Populations to be Analyzed:

Conditions or Focus of Study

- Bereavement
- Emotions
- Emotion Regulation
- Psychophysiology
- Social Affective Neuroscience

Eligibility Criteria

Inclusion Criteria:

- Recent bereavement of loved one (i.e. loss of romantic partner within the past 5-7 months)
- At least 18 years of age, with no maximum age, provided all other inclusion and exclusion criteria are met.
- Minimum score of 25 on the Inventory for Complicated Grief

- Must be able to speak, read, and write in English
- Must be eligible to safely complete MRI scanning

Exclusion Criteria:

- Death of a second close family member/friend in the past year
- If they are currently receiving psychotherapy
- If they have obstructive pulmonary and/or heart disease, diabetes, liver failure, or kidney failure
- If they have a significant visual, auditory, or cognitive impairment that compromises their ability to understand and complete the task
- If they've gotten divorced within the past year
- Prior participation in similar emotion regulation training protocol in [name] lab
- If they have any contraindication to MRI scanning (i.e. pregnancy, presence of any non-removable metal on or in the body, implanted medical devices, tattoos, medication patches, orthodontic braces or permanent retainers, hearing aids, and history of claustrophobia or breathing disorders)

Data Analysis:

All Outcomes

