Data analysis will primarily use linear mixed models, incorporating fixed effects for Training Group (Distancing and Reinterpretation), Session (T1-T5), and Trial Type (for analyses involving the reappraisal task; Look Neutral, Look Negative, and Reappraise Negative), and their interactions, as well as a random effect consisting of an intercept for each participant. In each analysis, statistically significant and near-significant intercept variance reflects reliable differences between participants. We will examine additional models that incorporate and estimate random-effects slope variance across participants on the time effect (i.e., Session). Outcome variables will be repeated measures in self-reported negative affect, RSA⁵, and neural activity (Aim 1) and changes in health-relevant behavioral outcomes (e.g., depressive symptoms and grief rumination; Aims 2 and 3). In these analyses, gender, age, baseline depressive symptoms, expectedness of the loss, and current (non-excluded) medication use will be incorporated as covariates. Importantly, given that we anticipate enrolling an approximately equal number of men and women, we also anticipate having sufficient power to conduct exploratory analyses on the effect of gender (and age) on the hypothesized effects (all Aims). Further, Aim 3 will be investigated using multilevel mediation modeling^{6,7} involving training group assignment as the higher-level predictor (X); self-reported negative affect, RSA data, and neural activity as potential individual-level mediators (M); and health-relevant behavior (i.e., depressive symptoms and grief rumination) as individual-level outcome variables (Y). Note that this will model mediation as a time-dependent and experimental process, both of which help

to rule out alternative explanations. Other exploratory model paths will also be tested. Appropriate covariates indicated above will be incorporated in all mediation models.

Data and Safety Monitoring Plan:

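### The SAP's 90% between-group power reproduces only with a one-sided test, which neither document declares; an unadjusted two-sided comparison on the same inputs has about 83%.

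*SAP*

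**What the plan says.** The SAP's Power Analyses section has four blocks: self-reported negative affect, RSA, neural activity, and "questionnaire outcomes (i.e., depressive symptoms, grief rumination, perceived stress, and reappraisal usage frequency" as a fourth group. Each uses d=.70, alpha .05 and 36 analysable participants per cell (42 recruited, 15% attrition). The first two blocks state "90% power ($\alpha=.05$) to detect between-group effects should be achieved with 36 participants per cell". The fMRI and questionnaire blocks state "90% power ($\alpha=0.05$) to detect between-group effects should be achieved with 36 participants per cell". Each block also claims over 95% power for within-group effects. No block gives the side of the test, the between-group contrast, the SD in which d is expressed, a within-person correlation or a covariate R-squared.

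The hypotheses under Specific Aims differ in how far they state a direction between the groups:

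- Aim 1 (negative affect, RSA, neural activity) expects changes under distancing "that are greater than those for reinterpretation training".
- Aim 2, on depressive symptoms and grief rumination, pools the groups: "Across time and participants, reductions in self-reported negative affect, increases in RSA, and changes in neural activity are expected to lead to reductions".
- Aim 3, which is exploratory, says "Distancing training will lead to reductions in grief rumination and depression that are mediated by changes in the targeted neurobiological and behavioral mechanisms". That sentence names no comparator, but the Data Analysis section makes training group the predictor in the mediation model for these two outcomes.
- Perceived stress and reappraisal frequency have no stated direction between the groups.

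The Data Analysis section plans "linear mixed models, incorporating fixed effects for Training Group (Distancing and Reinterpretation), Session (T1-T5" and, for task data, trial type) with interactions and a random intercept per participant. It adds: "In these analyses, gender, age, baseline depressive symptoms, expectedness of the loss, and current (non-excluded) medication use will be incorporated as covariates".

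**The concern.** When a plan gives alpha as .05 and says no more, most readers will assume a two-sided test. On that assumption the stated inputs do not give 90%. Aim 1, which covers the primary mechanism endpoints, is a question about the difference between the two trainings, so this is the power figure that matters most.

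Two things are at stake. First, a null between-group result could be read against a 10% type II risk when the unadjusted two-sided comparison has about 17% (100% - 83.4%). Second, with the side unwritten, the significance criterion is open. For a simple two-group contrast at 36 per cell, an observed d between 0.39 and 0.47 in the hypothesised direction is significant one-sided and not two-sided. That choice should not be available after the data are seen.

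**Working it through.** **Inputs (SAP, Power Analyses, the same in all four blocks).** d = 0.70; alpha = .05; n = 36 per cell. Attrition: 42 x 0.85 = 35.7, about 36.

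**Method.** Two independent groups, noncentral t, df = 2n - 2 = 70, noncentrality = d x sqrt(n/2) = 0.70 x sqrt(18) = 2.970.

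**Reproducing the plan's figure.**

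- One-sided: critical t = 1.667, power = 90.3%. At n = 35 it is 89.5%, so 36 is the smallest n that reaches 90%.
- Two-sided: critical t = 1.994, power = 83.4%.
- The normal approximation gives 90.7% and 84.4%, so the choice of formula does not close the gap.
- Within-group, paired, n = 36: 98.3% two-sided. The claim of over 95% holds with either side.

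**Two-sided power at other group sizes, d = 0.70.**

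| Analysable per cell | Power |
|---|---|
| 36 (15% attrition) | 83.4% |
| 38 (about 10% attrition, 42 x 0.90 = 37.8) | 85.4% |
| 42 (no attrition) | 88.7% |
| 43 | 89.4% |
| 44 | 90.1% |

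**Minimum detectable d at 36 per cell, two-sided.** 0.67 for 80% power and 0.77 for 90%.

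**Observed d needed for significance at 36 per cell.** Critical t x sqrt(2/36): 1.667 x 0.2357 = 0.39 one-sided; 1.994 x 0.2357 = 0.47 two-sided.

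**Why the contrast and the SD must be named.** If the contrast is a T1-T5 change and d is in change-score SD units, 83.4% carries over. If d is in raw-score SD units, the effective d is 0.70/sqrt(2(1 - r)), where r is the T1-T5 correlation. The documents give no r. Under assumed values with equal variances, two-sided power is:

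| r | 0.3 | 0.4 | 0.5 | 0.6 | 0.7 |
|---|---|---|---|---|---|
| Power | 70% | 76% | 83% | 91% | 97% |

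**What the planned model might add or cost (all assumptions, two-sided, 36 per cell).**

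- Covariates, effective d = 0.70/sqrt(1 - R2): R2 = 10%, 18% and 30% give 87%, 90% and 94%.
- A one-degree-of-freedom Group x linear Session slope over T1-T5, with a random intercept only, linear divergence and d = 0.70 for the T1-T5 change: noncentrality 3.32, power about 91%. Five sessions exist for negative affect, RSA and the PSS. fMRI is at T1 and T5 only; CES-D, UGRS and ERQ are at T1, T5 and the two follow-ups.
- With Session as a five-level factor, Group x Session is a 4-df F test. Under the same slope assumptions, with noncentrality 3.32 squared = 11.0 and 280 denominator df, power is about 76%. Such a test has no one-sided form.

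**The case against.** **The SAP never says the test was one-sided.** Correct. A reader might conclude that the 90% is known to come from a one-sided test, or that it is a miscalculation. The documents establish neither. Two-sided 90% would also follow from covariates explaining about 18% of the variance, and the Data Analysis section does plan covariates. But no such value is among the power inputs, and 36 is exactly the one-sided threshold, so the one-sided reading stays the likeliest.

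**83% is not the power of the planned analysis either.** This stands. The planned analysis is a covariate-adjusted mixed model, and the assumptions above move the figure in both directions. So 83% should be reported only for a named one-degree-of-freedom unadjusted contrast with d in its own SD units, and the contrast has to be fixed before any figure is restated. The same limit applies to the 0.39-0.47 band.

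**Directional hypotheses justify one-sided tests.** A directional hypothesis is not a test specification. The argument is open to Aim 1. For depressive symptoms and grief rumination, Aim 3 read with the mediation model arguably implies a direction between the groups, though it is exploratory and mediated. For perceived stress and reappraisal frequency there is none to appeal to.

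**The stakes are small.** Largely accepted. This is a Phase I, Stage I mechanism trial, no passage says that null results will be judged against a 10% type II risk, and none proposes one-sided testing at analysis.

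**Conclusion.** The concern holds in a limited form. The stated 90% is not supported for a conventional two-sided .05 test: on the SAP's own inputs, the unadjusted comparison has 83.4%, a shortfall of 6.6 points from 90%. The same gap appears in all four blocks. Neither lower attrition nor full retention closes it (85.4% and 88.7%), and the planned covariates and repeated measures cannot be credited without a correlation or R-squared that the SAP does not give.

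A reader might infer that the trial is underpowered or needs more participants. The documents do not support that: the unadjusted two-sided figure is above 80%, the planned model may do better, and the within-group claim stands. The conclusion rests on an unadjusted two-group t-test with d = 0.70 in the SD units of the contrast tested. The arithmetic is certain; the one-sided origin of the 90% is an inference. The consequence is modest, but the criterion should be in writing before group comparisons are run.

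**What to change.** In each of the four power blocks, in this order:

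1. Name the between-group contrast (for example, the one-degree-of-freedom difference between groups in T1-T5 change) and say whether d is in raw-score or change-score SD units.
2. State that between-group tests are two-sided at .05.
3. Replace 90% with about 83% for a one-degree-of-freedom unadjusted contrast with d in that contrast's SD units, and add the minimum detectable d (0.67 at 80% power, 0.77 at 90%). Alternatively, give the correlation or covariate R-squared that supports a higher figure. Note that a multi-degree-of-freedom Group x Session test would have different power.

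If one-sided tests were intended and no group comparison has been run, the SAP can declare them instead. It should then keep 90% only for contrasts with a direction between distancing and reinterpretation stated in advance. Those are negative affect, RSA and neural activity. Depressive symptoms and grief rumination qualify only if the direction implied by Aim 3 and the mediation model is written out as a between-group hypothesis. Perceived stress and reappraisal frequency take the two-sided figure. If comparisons have already been run, use the two-sided version.

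The cost is wording in four paragraphs, with no added participants, visits or measurements. The downside is a less favourable stated power or, under the one-sided option, giving up any claim in the opposite direction.

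### The fMRI power figures rest on the size of an amygdala response, while Aim 1 tests a between-arm difference in its change; the SAP gives no effect size for that contrast and none for DLPFC.

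*SAP*

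**What the plan says.** In the SAP, Power Analyses, Outcome: Neural activity (fMRI), the planning value is a "within-subject fMRI effect size estimate for right amygdala affective reactivity", taken from a meta-analysis of Human Connectome Project data and put at about d=.70. One sentence, with a reference, carries it over to the comparison of arms: "This effect size estimate is also appropriate for between-subjects neural effects". From this single value the SAP states over 95% power for within-group effects and "90% power ($\alpha=0.05$) to detect between-group effects", both with 36 analysable participants per cell out of 42 recruited.

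The neural hypothesis is in the SAP, Specific Aims, Aim 1. It expects "reductions in amygdala activity, increases in DLPFC activity" over time, and expects these changes to be larger with distancing than with reinterpretation. The SAP's Data Analysis section fits a linear mixed model with Training Group, Session, Trial Type and their interactions, and a random intercept per participant. According to the Protocol, Design, fMRI is collected at T1 and T5 only. The SAP Introduction lists neural mechanisms among the primary endpoints, and Aim 3 uses neural activity as a possible mediator.

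**The concern.** Reactivity is the size of a response. Aim 1 concerns how far that activity changes between two scans, and how much that change differs between two active arms. In the model this is Group x Session, or Group x Session x Trial Type. Its standardised size depends on the amount of change and on the SD of change, and neither follows from the size of the response alone.

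The SAP shows no step from one quantity to the other. The paragraph on self-reported negative affect, by contrast, takes its d from longitudinal reappraisal training data, which is the right kind of input. DLPFC is named in the hypothesis, but the only effect size given is for the right amygdala.

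At stake is how a neural result will be read. If no Group x Session effect is found, the stated 90% would invite the conclusion that a relevant effect was unlikely to have been missed. That power was not shown for the contrast tested.

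**Working it through.** **Inputs from the SAP.** d = 0.70; alpha = 0.05, sidedness not stated; 36 per cell after attrition (42 × 0.85 = 35.7).

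**Reproducing the stated figures (noncentral t, n = 36 per cell, d = 0.70).**
- Within-group, paired t: 98.3% two-sided, which agrees with over 95%.
- Between-group, two-sample t: 90.3% one-sided and 83.4% two-sided. The stated 90% is matched only by a one-sided test.

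So the SAP's figures are what results from entering 0.70 directly as the effect size for both comparisons.

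**Assumptions not in the documents.**
- Mean reactivity R is 0.70 SD at one scan in this task and sample, with the same SD at T1 and T5.
- r, the T1-T5 correlation of the response, is varied from .2 to .9.

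**Carrying reactivity over to change.** The SD of the T5-T1 change is SD × sqrt(2(1−r)). If the arms differ in change by a fraction f of R, then

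d_change = f × 0.70 / sqrt(2(1−r)).

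Setting d_change = 0.70 gives f = sqrt(2(1−r)). With adjustment for the T1 value, the residual SD is SD × sqrt(1−r²), so f = sqrt(1−r²). T1 neural activity is not among the covariates listed in the SAP, so the change-score column is closer to the planned model.

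For f = 1/2, d_change = 0.35 / sqrt(2(1−r)); at r = .5 this is 0.35. Power with 36 per cell follows from the two-sample t.

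| r | f needed for d = .70, change score | f needed, T1-adjusted | Power at f = 1/2, change score, two-sided | same, one-sided |
|---|---|---|---|---|
| .2 | 126% | 98% | 21% | 31% |
| .5 | 100% | 87% | 31% | 43% |
| .7 | 77% | 71% | 47% | 60% |
| .8 | 63% | 60% | 64% | 75% |
| .9 | 45% | 44% | 91% | 95% |

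**Within-group change.** At r = .5, a within-arm fall of half the response also has d = 0.35. The paired t with n = 36 then gives 53% two-sided, against the stated over 95%.

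**Detectable difference.** For 90% two-sided power with 36 per cell, d must be 0.775. As a share of R this is (0.775/0.70) × sqrt(2(1−r)): 140%, 111%, 86%, 70% and 50% at the same five values of r.

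**The case against.** The strongest objection is that the size of the problem depends on two quantities that the documents do not give.

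- **The correlation r.** At r = .9, a half-response difference between arms does have about 90% power. This stands, and is why a range is shown.
- **The reactivity of 0.70 SD.** It comes from Human Connectome Project data. This trial shows grief-themed images to bereaved people scoring at least 25 on a complicated-grief inventory. If R were 1.0 SD, the share needed for d = .70 would be 0.70 × sqrt(2(1−r))/1.0, or 70% at r = .5 and 54% at r = .7. A smaller R would raise it. This also stands, although the SAP itself carries 0.70 over.

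Three stronger readings are tempting, and the documents do not support them.

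- A reader might infer that distancing must abolish essentially the whole response. That follows only at r of about .5 or below, and only if reinterpretation changes nothing, since the comparison is between two active arms.
- A reader might infer that reactivity is a ceiling on what training can remove. Aim 1 does not fix the contrast, the model has three trial types, and nothing in the documents says that activity cannot fall below the reference condition.
- A reader might infer that the over-95% figure is simply wrong. The SAP does not define within-group effects. If they include a trial-type contrast at one scan, the figure follows from d=.70.

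The SAP also cites a reference for between-subjects use, whose content cannot be judged here. What can be said is that the SAP shows no derivation. Finally, this is a Phase I, Stage I mechanistic study and the remedy is a matter of wording, which bears on how serious the point is.

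**Conclusion.** The point holds in a limited form. The input to the fMRI power calculation is a response, the tested effect is a between-arm difference in change, and nothing in the SAP links the two. The stated 90%, and the over-95% where it is read as power for training change, are therefore not supported by the SAP's own input. No power basis exists for DLPFC.

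How far the figures overstate power is conditional on 0.70 SD reactivity carrying over and on r. Among the values tabulated, a half-response advantage for distancing reaches 90% only at r = .9; at r = .8 it has 64% two-sided or 75% one-sided. The documents do not establish that the neural comparison is underpowered, because they give neither r nor an expected change. They establish only that adequate power has not been shown.

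This is an unjustified effect-size assumption for a primary endpoint. It should be corrected, but it is not a must-fix defect.

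**What to change.** Change the SAP's fMRI power paragraph as follows.

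- Limit the over-95% figure to detecting affective reactivity itself within participants.
- Withdraw the 90% between-group figure, and withdraw the over-95% figure as power for training change.
- State instead the detectable Group x Session difference with 36 per cell, as a share of T1 reactivity, over a stated range of r (for example .2 to .9). Label r and the 0.70 SD reactivity as assumptions, and say whether the test is one- or two-sided.
- State that no power is claimed for DLPFC.

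The cost is a less favourable statement of neural power. No extra participants are needed and the analysis model is unchanged.

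### The SAP's 90% between-group power at d=.70 is reproduced for a simple two-sample test only one-sided (two-sided: 83%), and d=.70 is not justified as a difference between two active trainings

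*SAP*

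**What the plan says.** The SAP's Power Analyses section has four paragraphs: self-reported negative affect, RSA, fMRI and questionnaires. Each uses one approximate effect size, d=.70, for two purposes. Each states over 95% power for within-group effects and 90% for between-group effects at alpha .05 with 36 participants per arm. The questionnaire paragraph, for example, states "90% power ($\alpha=0.05$) to detect between-group effects should be achieved with 36 participants per cell". None says whether the test is one- or two-sided.

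The sources given for d=.70 differ:

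- **Negative affect:** "previously reported for within and between-subjects behavioral analyses of longitudinal reappraisal training data".
- **RSA:** "previously obtained for within and between-subjects analyses of RSA data".
- **Questionnaires:** "previously reported for within and between-subjects analyses of questionnaire reports measuring these variables".
- **fMRI:** a "within-subject fMRI effect size estimate for right amygdala affective reactivity", followed by the statement "This effect size estimate is also appropriate for between-subjects neural effects".

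The two arms are distancing training and reinterpretation training. The protocol's Objectives present these as the two main tactics of reappraisal, and its Design and Methods give both arms the same five-session schedule and task. There is no inert control. Aim 1 in the SAP expects distancing to produce larger changes than reinterpretation in negative affect, RSA and neural activity.

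**The concern.** There are two problems. First, the 90% does not come out of the SAP's inputs under a conventional two-sided test, and nothing in the SAP declares a one-sided one.

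Second, a within-group effect and a difference between two active trainings are different quantities. If both trainings work, the difference between them is smaller than the larger of the two effects on the same scale. The SAP gives no expected effect for reinterpretation and does not name the SD that standardises d. It also does not say whether its between-subjects sources compared two active trainings. A reader therefore cannot tell why .70 is a plausible between-arm difference.

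This matters most for Aim 1, whose comparative hypothesis is between arms and whose outcomes are the primary endpoints. A reader who relies on 90% power could take a null Group by Session result as good evidence that the trainings do not differ. The SAP does not draw that inference, but its power statement invites it.

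**Working it through.** **Inputs from the SAP.** d=.70; alpha .05; 42 recruited per arm; 15% attrition; 36 analysable per arm. Attrition check: 42 × 0.85 = 35.7, about 36, as stated.

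**Within-group power.** Paired t-test, n=36, noncentrality .70 × √36 = 4.20. Power is 98.3% two-sided and 99.3% one-sided. The stated figure of over 95% is reproduced either way, so it does not reveal the sidedness.

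**Between-group power.** Two-sample t-test, 36 per arm, df = 2 × 36 − 2 = 70, noncentrality .70 × √(36/2) = 2.97.

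- One-sided .05: 90.3% (normal approximation 90.7%). This reproduces the stated 90%.
- Two-sided .05: 83.4% (normal approximation 84.4%). This does not.

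Two-sided 90% at d=.70 needs 44 completers per arm (43 by normal approximation). Even with no attrition, 42 per arm would give 88.7%. Solving for d at 36 per arm, two-sided, gives .67 for 80% power and .77 for 90%.

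**If reinterpretation also has an effect.** The documents give no figure for it, so this is a range of scenarios. Assume a distancing within-arm d of .70 and one SD of change shared by both arms. Then between-arm d = .70 − reinterpretation d.

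| Reinterpretation d | Between-arm d | Power, two-sided | Power, one-sided |
|---|---|---|---|
| 0 | .70 | 83% | 90% |
| .20 | .50 | 55% | 68% |
| .35 | .35 | 31% | 43% |
| .50 | .20 | 13% | 21% |

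**Sensitivity to the standardiser.** Suppose the between-arm .70 is in units of the raw SD and the comparison is of change scores. Then d on the change SD is .70 / √(2(1 − ρ)), where ρ is the pre-post correlation. For ρ of .3, .5 and .7 this is .59, .70 and .90, with two-sided power of 70%, 83% and 97%. With adjustment for the outcome's own baseline instead, d becomes .70 / √(1 − ρ²), and two-sided power is 87%, 89% and 92% for ρ of .3, .4 and .5. The SAP gives no ρ, so none of these can be chosen.

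**The case against.** The strongest reply is that power is always conditional on a planning effect. The SAP powers two contrasts separately at an approximate .70 and never says that each arm will change by that amount. For three of the four outcome groups it claims a source that covered between-subjects analyses. Aim 1 is directional, and one-sided the 90% is right. The planned analysis is a mixed model with repeated sessions and covariates, which could do better than a t-test.

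Much of this stands. A reader might infer that a between-arm .70 is possible only if reinterpretation does nothing, or that the two uses of .70 contradict each other. The documents do not support that. It would require distancing's within-arm effect to be exactly .70 and both d values to share one SD of change; the SAP states neither. A between-arm .70 also follows from .90 against .20, or 1.05 against .35. Nor does the subtraction apply to the fMRI figure, which describes a task response and not a change with training.

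Three things remain. A directional hypothesis is not a declared one-sided test. A between-subjects source is not shown to be a comparison of two active trainings, and the cited sources cannot be checked here. The possible gain from the mixed model rests on correlations that the SAP does not give; as the sensitivity figures show, the standardiser can move power either way.

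**Conclusion.** The point holds in limited form. For a simple two-sample comparison at 36 per arm and d=.70, power is 83.4% two-sided; the stated 90% requires a one-sided test that the SAP does not declare. This applies to all four paragraphs and needs no assumption about reinterpretation.

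Separately, d=.70 is not justified as a difference between two active trainings. The gap is clearest for fMRI, where a within-subject reactivity estimate is carried over to between-subjects effects by assertion. For the other outcomes the two uses are unreconciled, which is less than contradictory.

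Power of 55%, 31% or 13% is conditional on the scenarios shown: distancing at .70, a shared SD of change, and reinterpretation at .20, .35 or .50. A reader might conclude from these that the trial is shown to be underpowered. It is not: the true between-arm difference is unknown, and power under the planned mixed model cannot be computed from the documents.

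**What to change.** Keep N. In each of the four power paragraphs, and most importantly for the Aim 1 outcomes (negative affect, RSA, fMRI), replace the between-group statement with wording such as:

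> With 36 per arm and two-sided alpha .05, a simple two-sample comparison of change has 83% power for d=.70, 80% for d=.67 and 90% for d=.77; power is 55%, 31% and 13% for between-arm differences of .50, .35 and .20. The mixed model with covariates may differ.

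State which SD standardises d. If a one-sided test is intended, say so and justify it, and give the one-sided figures instead (90% at .70; 68%, 43% and 21% at .50, .35 and .20). In the fMRI paragraph, do not present the reactivity estimate as support for a difference between trainings.

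The cost is SAP wording only. The drawback is that the stated power becomes less favourable.
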